13.2 Administrative Requirements

13.2.1 Ethical Considerations

The study will be conducted in accordance with the current ICH GCP Guidelines, which are consistent with the ethical principles founded in the Declaration of Helsinki, and in accordance with local applicable laws and regulations. The IRB/IEC will review all appropriate study documentation to safeguard the rights, safety, and well-being of the subjects. The study will only be conducted at sites where IRB/IEC approval has been obtained. The protocol, Investigator's Brochure, sample ICF, advertisements (if applicable), written information given to the subjects (including diary cards), safety updates, annual progress reports, and any revisions to these documents will be provided to the IRB/IEC by the investigator or Vertex, as allowable by local applicable laws and regulations.

13.2.2 Subject Information and Informed Consent

The investigator (or an appropriate authorized designee) will obtain informed consent from each subject before any study procedure takes place. The method of obtaining and documenting the informed consent and the contents of the consent will comply with ICH GCP and all applicable laws and regulations and will be subject to approval by Vertex or its designee.

13.2.3 Investigator Compliance

No modifications to the protocol will be made without the approval of both the investigator and Vertex. Changes that significantly affect the safety of the subjects, the scope of the investigation, or the scientific quality of the study (i.e., efficacy assessments) will require IRB/IEC notification before implementation, except where the modification is necessary to eliminate an apparent immediate hazard to human subjects. Vertex will submit all protocol modifications to the required regulatory authorities.

When circumstances require an immediate departure from procedures set forth in the protocol, the investigator will contact Vertex to discuss the planned course of action. If possible, contact will be made before the implementation of any changes. Any departures from the protocol will be fully documented in the source documentation and in a protocol deviation log.

13.2.4 Access to Records

The investigator will make the office and/or hospital records of subjects enrolled in this study available for inspection by Vertex or its representative at the time of each monitoring visit and for audits. The records will also be available for direct inspection, verification, and copying, as required by applicable laws and regulations, by officials of the regulatory health authorities (FDA and others). The investigator will comply with applicable privacy and security laws for use and disclosure of information related to the research set forth in this protocol.

13.2.5 Subject Privacy

To maintain subject confidentiality and to comply with applicable data protection and privacy laws and regulations, all CRFs, study reports, and communications relating to the study will identify subjects by assigned subject numbers and access to subject names linked to such numbers shall be limited to the site and the study physician and shall not be disclosed to Vertex. As required by applicable laws and regulations in the countries in which the study is being conducted, the investigator will allow Vertex and/or its representatives access to all pertinent medical records to allow for the verification of data gathered in the CRFs/SAE forms and the

review of the data collection process. The FDA and regulatory authorities in other jurisdictions, including the IRB/IEC, may also request access to all study records, including source documentation, for inspection.

For sites participating in the study in the US, and in accordance with the Health Insurance Portability and Accountability Act and associated regulations (“HIPAA”) an executed HIPAA authorization shall be obtained by the site from each subject (or the legal representative of the subject) before research activities may begin. Each HIPAA authorization shall comply with all HIPAA requirements including authorization allowing the site access to and use of the subject’s personally identifiable health information, authorization for the site to disclose such information to Vertex, the FDA, and other parties requiring access under the protocol, and statements as to the purpose for which such information may be used and for how long.

13.2.6 Record Retention

The investigator will maintain all study records according to ICH GCP guidelines and/or applicable local regulatory requirement(s), whichever is longest, as described in the Clinical Trial Agreement. If the investigator withdraws from the responsibility of keeping the study records, custody will be transferred to a person willing to accept the responsibility and Vertex will be notified.

13.2.7 Study Termination

At any time, Vertex may terminate this study in its entirety or may terminate this study at any particular site. In addition, for reasonable cause, either the investigators or their IRBs/IECs may terminate the study at their center.

Conditions that may lead to reasonable cause and warrant termination include, but are not limited to:

- Subject or investigator noncompliance
- Unsatisfactory subject enrollment
- Lack of adherence to protocol procedures
- Lack of evaluable and/or complete data
- Potentially unacceptable risk to study subjects
- Decision to modify drug development plan
- Decision by the FDA or other regulatory authority

Written notification that includes the reason for the clinical study termination is required.

13.3 Data Quality Assurance

Vertex or its designated representative will conduct a study site visit to verify the qualifications of each investigator, inspect clinical study site facilities, and inform the investigator of responsibilities and procedures for ensuring adequate and correct study documentation.

The investigator is required to prepare and maintain adequate and accurate case histories designed to record all observations and other data pertinent to the study for each study participant. Study data for each enrolled subject will be entered into a CRF by study site

personnel using a secure, validated, web-based electronic data capture (EDC) application. Vertex will have read-only access to site-entered clinical data in the EDC application.

Instances of missing, discrepant, or uninterpretable data will be queried with the investigator for resolution. Any changes to study data will be made to the CRF and documented in an audit trail, which will be maintained within the clinical database.

13.4 Monitoring

Monitoring and auditing procedures developed or approved by Vertex will be followed to comply with GCP guidelines. On-site checking of the CRFs/SAE Forms for completeness and clarity, cross-checking with source documents, and clarification of administrative matters will be performed.

The study will be monitored by Vertex or its designee. Monitoring will be done by personal visits from a representative of Vertex, or designee (study site monitor), who will review the CRFs/SAE Forms and source documents. The study site monitor will ensure that the investigation is conducted according to the protocol design and regulatory requirements.

13.5 Electronic Data Capture

Vertex will provide the study sites with secure access to and training on the EDC application sufficient to permit study site personnel to enter or correct information in the CRFs on the subjects for which they are responsible.

A CRF will be completed for each enrolled study subject. It is the investigator's responsibility to ensure the accuracy, completeness, clarity, and timeliness of the data reported in the subject's CRF. Source documentation supporting the CRF data will indicate the subject's participation in the study and will document the dates and details of study procedures, AEs, other observations, and subject status.

The investigator, or designated representative, will complete the CRF as soon as possible after information is collected.

The audit trail entry will show the user's identification information and the date and time of any correction. The investigator will provide formal approval of all the information in the CRFs, including any changes made to the CRFs, to endorse the final submitted data for the subjects for whom the investigator is responsible.

Vertex will retain the CRF data and corresponding audit trails. A copy of the final archival CRF in the form of a CD or other electronic media will be placed in the investigator's study file.

13.6 Publications and Clinical Study Report

13.6.1 Publication of Study Results

Any and all scientific, commercial, and technical information disclosed by Vertex in this protocol or elsewhere will be considered the confidential and proprietary property of Vertex. The investigator shall hold such information in confidence and shall not disclose the information to any third party except to such of the investigator's employees and staff as have been made aware that the information is confidential and who are bound to treat it as such and to whom disclosure is necessary to evaluate that information. The investigator shall not use such information for any purpose other than determining mutual interest in performing the study and, if the parties decide to proceed with the study, for the purpose of conducting the study.

The investigator understands that the information developed from this clinical study will be used by Vertex in connection with the development of the study drug and other drugs and diagnostics, and therefore may be disclosed as required to other clinical investigators, business partners and associates, the FDA, and other government agencies. The investigator also understands that, to allow for the use of the information derived from the clinical study, the investigator has the obligation to provide Vertex with complete test results and all data developed in the study.

No publication or disclosure of study results will be permitted except under the terms and conditions of a separate written agreement between Vertex and the investigator and/or the investigator's institution.

13.6.2 Clinical Study Report

A clinical study report, written in accordance with the ICH E3 Guideline, will be submitted in accordance with local regulations.

The clinical severity criteria (average sweat chloride >86 mmol/L and %PI >50%) do not apply to the individual subjects to be enrolled in this study, but were used to classify the mutation status on a population level.

The list below represents acceptable mutations, which are detectable by an FDA-cleared genotyping assay; however, this list may not include every eligible mutation, and investigators should contact the medical monitor regarding other mutations that may also meet study eligibility criteria.

CFTR Mutations Eligible for VX16-659-101, Part 1 and Part 3

Criteria	Mutation				
Truncation mutations	S4X	C276X	G542X	R792X	E1104X
• %PI >50% and/or SwCl ⁻ >86 mmol/L	G27X	Q290X	G550X	E822X	R1158X
• no full-length protein	Q39X	G330X	Q552X	W846X	R1162X
	W57X	W401X	R553X	Y849X	S1196X
	E60X	Q414X	E585X	R851X	W1204X
	R75X	S434X	G673X	Q890X	L1254X
	E92X	S466X	Q685X	S912X	S1255X
	Q98X	S489X	R709X	Y913X	W1282X
	Y122X	Q493X	K710X	W1089X	Q1313X
	E193X	W496X	L732X	Y1092X	E1371X
	L218X	C524X	R764X	W1098X	Q1382X
	Q220X	Q525X	R785X	R1102X	Q1411X
Splice mutations	185+1G→T	711+5G→A	1717-8G→A	2622+1G→A	3121-1G→A
• %PI >50% and/or SwCl ⁻ >86 mmol/L	296+1G→A	712-1G→T	1717-1G→A	2790-1G→C	3500-2A→G
• no or little mature mRNA	405+1G→A	1248+1G→A	1811+1G→C	3040G→C (G970R)	3600+2insT
	405+3A→C	1249-1G→A	1811+1.6kbA→G		3850-1G→A
	406-1G→A	1341+1G→A	1812-1G→A	3120G→A	4005+1G→A
	621+1G→T	1525-2A→G	1898+1G→A	3120+1G→A	4374+1G→T
	711+1G→T	1525-1G→A	1898+1G→C	3121-2A→G	
Small (≤3 nucleotide) insertion/deletion (ins/del)	182delT	1119delA	1782delA	2732insA	3876delA
frameshift mutations	306insA	1138insG	1824delA	2869insG	3878delG
• %PI >50% and/or SwCl ⁻ >86 mmol/L	365-366insT	1154insTC	2043delG	2896insAG	3905insT
• garbled and/or truncated protein	394delTT	1161delC	2143delT	2942insT	4016insT
	442delA	1213delT	2183AA→G ^a	2957delT	4021dupT
	444delA	1259insA	2184delA	3007delG	4040delA
	457TAT→G	1288insTA	2184insA	3028delA	4279insA
	541delC	1471delA	2307insA	3171delC	4326delTC
	574delA	1497delGG	2347delG	3659delC	
	663delT	1548delG	2585delT	3737delA	
	935delA	1609del CA	2594delGT	3791delC	
	1078delT	1677delTA	2711delT	3821delT	
Non-small (>3 nucleotide) insertion/deletion (ins/del)	CFTRdele2,3	1461ins4		2991del32	
frameshift mutations	CFTRdele22,23	1924del7		3667ins4	
• %PI >50% and/or SwCl ⁻ >86 mmol/L	124del23bp	2055del9→A		4010del4	
• garbled and/or truncated protein	852del22	2105-		4209TGTT→AA	
	991del5	2117del13insAGAAA			
		2721del11			

CFTR Mutations Eligible for VX16-659-101, Part 1 and Part 3

Criteria	Mutation			
Class II, III, IV mutations not responsive to IVA alone or in combination with TEZ or LUM	A46D ^b	V520F	Y569D ^b	N1303K
	G85E	A559T ^b	L1065P	
	R347P	R560T	R1066C	
	L467P ^b	R560S	L1077P ^b	

 • %PI>50% and/or SwCl >86 mmol/L 	I507del	A561E	M1101K	
AND				

 • Not responsive in vitro to IVA alone or in combination with TEZ or LUM 				

Source: CFTR2.org [Internet]. Baltimore (MD): Clinical and functional translation of CFTR. The Clinical and Functional Translation of CFTR (CFTR2), US Cystic Fibrosis Foundation, Johns Hopkins University, the Hospital for Sick Children. Available at: <http://www.cfr2.org/>. Accessed 15 February 2016.

CFTR: cystic fibrosis transmembrane conductance regulator; IVA: ivacaftor; LUM: lumacaftor; PI: pancreatic insufficiency; SwCl: sweat chloride; TEZ: tezacaftor

Note: %PI: percentage of *F508del-CFTR* heterozygous patients in the CFTR2 patient registry who are pancreatic insufficient; SwCl: mean sweat chloride of *F508del-CFTR* heterozygous patients in the CFTR2 patient registry

^a Also known as 2183delAA→G.

[figure not shown]
^b Unpublished data.

2 MODIFICATIONS

2.1 Modifications to the Approved Clinical Study Protocol

Key changes in the current version of the SAP are summarized below.

Change and Rationale	Affected Sections
Treatment-emergent (TE) period has been revised to be from first dose date of study drug in the Treatment Period until 28 days after the last dose date of study drug or end of study date (based on end of study visit in CRFs), whichever occurs first.	Section 8.1

2.2 Modifications to the Approved Statistical Analysis Plan

This is the 1st version of Statistical Analysis Plan for the final analysis.

2.3 Modifications to the Approved DMC Charter

Not Applicable.

3 INTRODUCTION

This statistical analysis plan (SAP) for the final analysis is based on the approved clinical study protocol (CSP), Version 3.0, dated 01 Sep 2017, approved electronic case report form (eCRF), Version 1.4, dated 10 Aug 2017, and approved eCRF completion guidelines, Version 1.0, dated 14 Jul 2017.

This SAP will be used to perform interim analyses (IAs) for each part after 50% of subjects in the part have completed the Day 15 Visit. In addition, this SAP will be used to perform final analysis that will occur after all subjects in each part have completed the Safety Follow-Up Visit.

This is a Phase 2, randomized, double-blind, placebo- and TEZ/IVA-controlled, parallel-group, multicenter study to evaluate the safety and efficacy of VX-659 combination therapy in subjects aged 18 years and older with cystic fibrosis.

This SAP (Methods) documents the planned statistical analyses of efficacy endpoints and safety endpoints.

Vertex Biometrics will perform the statistical analysis for each IA, and the final analysis. SAS[®] Version 9.4 or higher software [REDACTED] will be used to generate all statistical outputs (tables, figures, listings, and datasets).

The SAP (Methods) will be finalized and approved prior to the data cut for the first IA. Any revisions to the approved SAP will be documented and approved in an amendment to the SAP prior to the clinical database lock for the final analysis. Any changes made to the SAP Methods after the clinical database lock has occurred will be documented in the clinical study report for this study.

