12 STATISTICAL AND ANALYTICAL PLANS

This section presents a summary of the planned safety analyses and clinical pharmacology analyses for this study. Safety statistical analysis details will be provided in the statistical analysis plan (SAP) for this study, and clinical pharmacologic analysis details will be provided in the clinical pharmacology analysis plan (CPAP), both of which will be finalized before clinical database lock.

Final analyses will take place after all subjects have completed the study, all data have been entered in the clinical study database, and the database has been locked.

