12.3.6 Interim and IDMC Analyses

12.3.6.1 Interim Analysis

Interim analyses may be conducted for any part of the study after at least 50% of subjects in the part have completed the Day 15 Visit. Each IA will only include data for a single part of the study. The results of these analyses will be reviewed by a limited Vertex team. When an IA is performed after all subjects in a part have completed the Safety Follow-up Visit, results from that part will be unblinded for full review by the Vertex study team.

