9 INTERIM AND IDMC ANALYSES

9.1 Interim Analysis

A separate IA may be performed after all subjects in Part 1, Part 2, and Part 3 have completed the Safety Follow-up Visit. All data from the part will be unblinded after the data from that part are cleaned for analysis and a data cut is performed. The Vertex Study Team will be unblinded to the interim analysis results.

In addition, IAs may be performed for each part after 50% of subjects in the part have completed the Day 15 Visit. These results will be reviewed by a limited Vertex team.

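### Can a part's analysis rules be changed after the study team has seen its results, because SAP amendments stay open until the final database lock?

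*SAP*

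**What the plan says.** SAP section 3 says that the methods "will be finalized and approved prior to the data cut for the first IA". Any change to this "approved SAP will be documented and approved in an amendment to the SAP prior to the clinical database lock for the final analysis", and anything changed after that lock is reported in the clinical study report. Section 2.2 is where revisions to the SAP are recorded; it now reads "This is the 1st version of Statistical Analysis Plan for the final analysis".

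The two documents describe the final analysis differently. Protocol section 12 states: "Final analyses will take place after all subjects have completed the study". SAP section 3 speaks of a "final analysis that will occur after all subjects in each part have completed the Safety Follow-Up Visit", which can be read part by part.

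Both documents allow an interim once all subjects in a part have completed safety follow-up. Under Protocol section 12.3.6.1, "results from that part will be unblinded for full review by the Vertex study team". SAP section 9.1 gives the trigger: "All data from the part will be unblinded after the data from that part are cleaned for analysis and a data cut is performed". This interim is optional in both.

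On who does the work, the lists of unblinded parties in Protocol section 10.7.1 and SAP section 6.4.2 name a vendor as performing the interims. SAP section 3 says: "Vertex Biometrics will perform the statistical analysis for each IA, and the final analysis". SAP section 9.1.1, which covers only the interims held after half of a part has passed Day 15, sends treatment codes, spirometry and sweat chloride data to an unblinded Biometrics group of the sponsor. That group is on neither list.

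**The concern.** An amendment cut-off protects the analysis only if it falls before the people who can amend the plan know the results. Here the cut-off is a database lock, while knowledge can arrive at a data cut. If the lock is study-wide and one part is unblinded early, the study team could revise a rule for that part after seeing how it came out. The revision would pass as an ordinary amendment, because only changes after the lock must go into the clinical study report. A reader would have to infer the order of events from dates.

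The disagreement over the interims looks like a second weakness. If a sponsor group holds treatment codes while the study is running, one expects the blinding lists to name it. The limited sponsor team that reviews interim results is explicitly kept out of study conduct (Protocol section 10.7.2, SAP section 6.4.3). No such sentence covers the unblinded Biometrics group.

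**Working it through.** No stated figure needs reproducing; the check is of sequence and scope.

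**1. Which lock.** SAP section 3 names one lock. SAP section 9.1 calls the part-completion analysis an interim and triggers it by a data cut. With Protocol section 12, this favours the study-wide reading. The per-part reading would shrink or close the gap, so the study-wide reading is the harder case and is tested here.

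**2. What could still be amended on that reading.**

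| Item | Where fixed | Open to SAP amendment? |
|---|---|---|
| Primary ppFEV₁ model: terms, covariate, covariance structure and fallback, missing-data assumption | Protocol 12.3.3.1 | No |
| Part 1 sweat chloride trend test and its three contrasts | Protocol 12.1.2, Table 12-1 | No |
| General approach for CFQ-R | Protocol 12.3.3.2 | No |
| CFQ-R covariates | SAP 8.3.2.2 | Yes |
| Sweat chloride covariates | SAP 8.3.5.1 and 8.3.5.2; Protocol 12.3.4 leaves them general | Yes |
| Sweat chloride values below 10 or above 160 mmol/L set to missing | SAP 8.3.5 | Yes |
| Efficacy visit windows | SAP Appendix B | Yes |

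The visit windows apply to spirometry as well, so they reach the inputs of the primary model, though not the model itself.

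**3. How far the windows could move the primary analysis.** Day 15 and Day 29 visits are allowed ±2 days, that is days 15 − 2 = 13 to 15 + 2 = 17, and 29 − 2 = 27 to 29 + 2 = 31. The Day 15 window is [1, 22] in every part. The Day 29 window is (22, 36] in Part 2 and (22, 43] in Part 3. In Part 1 it is the nominal visit, or else (22, 31]. Every on-schedule visit falls inside its window, and Appendix B gives the scheduled measurement priority for efficacy. Moving a window edge would therefore affect only off-schedule or unscheduled values, unless the new edge cut into the protocol's own visit ranges.

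**4. How long the interval might be.** The protocol synopsis gives about 13, 20 and 12 weeks for Parts 1, 2 and 3. If the last subjects of all parts were screened together, Part 1 would finish 20 − 13 = 7 weeks and Part 3 20 − 12 = 8 weeks before Part 2. If every Part 2 subject skipped the 4-week follow-up, Part 2 would take 20 − 4 = 16 weeks and the gaps would be 16 − 13 = 3 and 16 − 12 = 4 weeks. That exemption applies only to subjects who came from Study 661-110 and return to it (Protocol section 9.1.5). Enrolment dates are not given, the parts differ in size (54, 27 and 24) and Part 3 is optional, so the gap could also be zero or reversed. The figures show that an interval can exist, not how long it is.

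**5. Protocol deviations.** The rules for important deviations are also final only before database lock (SAP section 8.2.6, Appendix D). A blinded team is to categorise them, and the output is a listing. SAP section 7 defines no per-protocol set, so a reclassified deviation removes nobody from an analysis.

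**6. Who runs the interims.** SAP section 9.1.1 has a blinded Biometrics group write the code and test it on dummy treatment codes, spirometry and sweat chloride data. A separate unblinded group produces the outputs and passes them straight to the limited sponsor team. The functions are separated, although the lists name a vendor.

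**The case for a change.** The strongest reply is that the cut-off hangs on the wrong event and that moving it would cost almost nothing. The sponsor could freeze the rules for each part before that part is unblinded and mark any later change as post hoc. The per-part reading does not fully rescue the text, since SAP section 9.1 unblinds on a data cut and no part-level lock is named. The visit windows touch the primary endpoint, so the exposure is not confined to secondary results. The deviation team in Appendix D includes the study biostatistician and the medical monitor; if they belong to the study team, they would no longer be blind to an unblinded part.

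Much of this stands as description. The text does not say which lock is meant, it sets no part-level cut-off, and the blinding lists do contradict SAP sections 3 and 9.1.1. What does not follow is that a result is at risk. Nothing in the plan directs anyone to change a rule after unblinding. The approved plan exists before any interim cut, and a label would add only what the amendment and unblinding dates already allow a reader to establish. The blinded-team requirement in SAP section 8.2.6 already implies that deviations for a part are categorised before the study team is unblinded to it. For the Biometrics group, the missing sentence is about documentation: its stated task is to run prepared programs and hand over the outputs.

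**Conclusion.** No change follows. The amendment cut-off is a gap that analysts fill sensibly: a methods change made after a part has been unblinded will be dated, and it can be read as post hoc from that date. The exposure arises only if the optional part-level interim is held, the lock is study-wide, and someone then amends one of four SAP-only items: visit windows, sweat chloride validity limits, sweat chloride covariates or CFQ-R covariates. The primary ppFEV₁ model and the Part 1 trend contrasts lie outside it. Followed as written, the plan gives the same estimates, tests and intervals with or without a part-level cut-off.

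The vendor and Biometrics discrepancy is a clerical slip in who is named. It opens no route to altered methods, and the study team's blind does not depend on it.

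This rests on two assumptions: that amendments are dated and logged as SAP sections 2.2 and 3 provide, and that the unblinded Biometrics group is kept apart in practice as SAP section 9.1.1 sets out.
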